## **7) OUTCOME MEASURES**

The aim of the study is to determine the feasibility, acceptability and preliminary effectiveness of the intervention designed. The benefits of answering this question would be that participants may experience improvement in their FND symptoms and potential improvement in quality of life as a result of this. Additionally, if the outcomes of the intervention are positive, this could inform future research conducted and further development of the designed intervention which would be able to help other individuals with FND in the future.

## **8) DATA COLLECTION, SOURCE DATA AND CONFIDENTIALITY**

Personally identifiable data will be collected about participants including their name, address, contact details, details of registered GP. Data around participants' FND symptoms, mental health and quality of life will also be collected and stored. These will be collected via interview and questionnaires delivered via Qualtrics survey. Treatment sessions will also be audio and video recorded to be monitored for quality in Clinical Supervision.

Therapy sessions will be recorded using Microsoft Teams using the Principal Investigator's University of Manchester Teams account. Following the session, recordings will immediately be transferred on to the principal researcher's University of Manchester secure P-Drive. Recordings will be deleted as soon as possible following the principal researcher receiving clinical supervision on the sessions recorded. Sessions will be stored on a University drive in mp4 format using password protection which will only be known by the research team. The research team will monitor to ensure that videos are password protected and are only being accessed for the purpose of supervision. The password will contain a minimum 7 characters, have a mixture of upper- and lower-case letters, symbols and numbers. The recording will be checked and then deleted from Teams. Consent forms and safety plans will be saved on the Research Data Storage system. The file name will be saved with a date of consent and allocated a number to protect confidentiality and ensure no file names are the same (i.e. DD\_MMM\_YYYY\_P\_1 or DD\_MMM\_YYYY\_CL\_1). Participants will be asked to complete measures throughout baseline, treatment and follow-up. These will be administered via Qualtrics survey. Participants will complete surveys under Unique ID codes and the data received from participants will therefore be stored under their Unique ID codes. Data from Qualtrics surveys will be stored on the P-Drive under the anonymised ID codes.

## **9) STATISTICAL CONSIDERATIONS**

### **9.1 Statistical Analysis**

To assess the primary aim (acceptability and feasibility), we will measure adherence to treatment, safety (adverse reactions) and attitude to intervention. We will conduct descriptive statistical analysis of: therapy completion rates, sessions attended, measures completed, adverse events and participant satisfaction with the therapy.

In order to assess the secondary hypothesis (efficacy of treatment) we will chart individual participant FND symptoms and clinical measures during the baseline and treatment phases to determine any change in these variables over the course of treatment. We will calculate Rate of Change Index (RCI) and Clinically Significant Change (CSC) for the various outcome measures to determine if the change seen is statistically reliable and clinically meaningful.

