## 2) INTRODUCTION

The current study will use a systematic case series design to pilot a manualised intervention for individuals with a diagnosis of Functional Neurological Disorder (FND). The study will recruit 8 participants and measure their FND symptoms, psychological wellbeing and

satisfaction with the treatment package delivered. Baseline measures will be collected during a pre-treatment meeting. Intervention will involve 6-8, 1-hour sessions delivered online via videocall. The intervention will aim to improve body perception by getting participants to ‘tune into’ (pay attention to) their body using different methods and in different physical and emotional states. The study will assess whether the treatment package is acceptable to participants and feasible to deliver. The study will also gather preliminary data around any changes in FND symptoms and psychological wellbeing to see if the intervention has the potential to improve clinical outcomes.

It is expected that the intervention delivered will be feasible and acceptable to deliver and successful in reducing participants’ FND symptoms. If this is the case, it would benefit both the participants of the study and people with FND in the future.

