## **4.2 Secondary Question/Objective:**

The secondary aim is an initial evaluation of the efficacy of the piloted treatment package including impact on psychological distress, core FND Symptoms and quality of life.

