### **5.2 Study Intervention and/or Procedures**

Treatment:

- Participants will be offered 8, 1-hour, online sessions, delivered weekly via Microsoft Teams. The intervention will focus on developing skills to improve attunement to the signals from the body to the brain.
- The sessions will involve engaging in various exercises tuning into the body under different circumstances. Participants will be asked to tune into how particular objects feel in their hands. Participants may be presented with short clips or stories to make them feel a little happy or sad and then will be asked to tune into how the body feels in response to them.
- These sessions will be recorded via Microsoft Teams and selected aspects of them will be observed by the principal researcher and their clinical supervisor to ensure therapy quality.
- Participants will be asked to complete weekly measures online via Qualtrics survey platform in the 10-15 minutes prior to their session commencing. Assessment measures (CORE-10, FND symptoms questions, EuroQol Dimension and a measure of adverse reactions to the therapy) will be completed weekly. Any adverse reactions will be addressed in the beginning of the session.
- In the final session of treatment, all the preliminary measures will be repeated along with the measures of satisfaction in therapy and intervention acceptability.
- Following the final session of treatment, a date to complete a one-month follow up will be arranged with the participant.

Follow-Up:

- One month following the end of psychological therapy, a session will be attended remotely via Microsoft Teams by participants.

- During this session, all pre-treatment, weekly and post-treatment measures will be re-administered including questionnaires measuring satisfaction with therapy.

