- Participants meeting all criteria and having completed the safety plan will complete baseline measures: CORE 34, 5 questions assessing FND symptoms, the Screening for Somatoform Symptoms 7 (SOMS-7) and the Work and Social Adjustment Scale (WSAS).
- Following completion of baseline measures, the first remote session to deliver the psychological intervention will be arranged with the participant.

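### Section 9.1 charts a baseline phase against a treatment phase, but only one or two pre-treatment readings are scheduled, so the secondary result is uncontrolled within-person change, not efficacy

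*Combined protocol and SAP*

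**What the plan says.** Section 4.2 sets the purpose: "The secondary aim is an initial evaluation of the efficacy of the piloted treatment package". Section 9.1 gives the method. The team will "chart individual participant FND symptoms and clinical measures during the baseline and treatment phases to determine any change in these variables", and then: "We will calculate Rate of Change Index (RCI) and Clinically Significant Change (CSC) for the various outcome measures". Section 8 also treats baseline as a period: "Participants will be asked to complete measures throughout baseline, treatment and follow-up".

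The schedule reads differently. Section 2 states: "Baseline measures will be collected during a pre-treatment meeting". Section 6.3 lists one completion: "Participants meeting all criteria and having completed the safety plan will complete baseline measures: CORE 34, 5 questions assessing FND symptoms", followed by SOMS-7 and WSAS. The next step is: "Following completion of baseline measures, the first remote session to deliver the psychological intervention will be arranged with the participant". No section gives a baseline length, a number of baseline occasions or a staggered start, and no control group is described.

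Section 5.2 adds one relevant detail: "Participants will be asked to complete weekly measures online via Qualtrics survey platform in the 10-15 minutes prior to their session commencing". The weekly set contains CORE-10, the FND questions, EuroQol and a measure of adverse reactions. Session 1 is not exempted, so the first weekly survey falls before any treatment.

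**The concern.** A chart of baseline against treatment is informative when the baseline shows how a person's scores were behaving beforehand: their level, their spread from one occasion to the next, and whether they were already moving. In an uncontrolled case series, that pre-treatment record is the only comparator each participant has. Section 9.1 relies on such a record, and the schedule does not collect one.

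Entry requires current FND symptoms (section 6.1), so some of those enrolled may be at a worse point than usual and may improve without treatment. If scores fall during the sessions, the planned charts cannot show whether the fall began earlier. What is at stake is the wording of the secondary conclusion: the plan would report efficacy from data that support only a before-and-after description. Pre-treatment readings that are not taken cannot be recovered later.

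**Working it through.** The plan states no alpha, power, effect size, SD or reliability for this analysis, and it justifies 8 participants by precedent. There is therefore no planned figure to reproduce. The check is a count of readings, followed by an illustration.

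**Step 1. Pre-treatment readings per measure (sections 6.3 and 5.2)**

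| Measure | Baseline completion | Survey before session 1 | Total |
|---|---|---|---|
| Five FND questions | 1 | 1 | 2 |
| CORE-10 | 0 | 1 | 1 |
| EuroQol | 0 | 1 | 1 |
| CORE 34 | 1 | 0 | 1 |
| WSAS | 1 | 0 | 1 |
| SOMS-7 | 1 | 0 | 1 (possibly 2) |

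The second SOMS-7 reading arises only if the eligibility items (34-47, section 6.1) are completed on a separate occasion; it would be partial. CORE 34 and CORE-10 are counted separately because the documents name them separately. No measure has three readings.

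**Step 2. What that number of points can show**

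A straight line through k points leaves k − 2 residual degrees of freedom. With weekly spacing and occasion-to-occasion SD s, the standard error of the slope is s / √Σ(t − t̄)².

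- k = 1: no slope and no within-person spread.
- k = 2: Σ(t − t̄)² = 0.5, so SE = 1.41s per week with 0 residual df. Two points give either a spread (if no trend is assumed) or a slope, but no check of one against the other. The gap between the meeting and session 1 is not stated; one week is assumed here.
- k = 3: Σ(t − t̄)² = 2, so SE = 0.71s per week with 1 residual df.
- k = 5: Σ(t − t̄)² = 10, so SE = 0.32s per week with 3 residual df.

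Three is the first number at which drift can be judged at all, and then only roughly.

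**Step 3. Whether RCI or CSC fills the gap**

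I read RCI as change divided by its measurement error, SD × √(2(1 − r)), with 1.96 as the threshold. The formula and threshold are assumptions, because section 9.1 gives neither. If treatment does nothing but scores improve by d SD anyway:

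P(classed as reliably improved) = 1 − Φ(1.96 − d / √(2(1 − r)))

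P(at least one of 8) = 1 − (1 − P)⁸

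| d (assumed) | r (assumed) | P per person | At least one of 8 |
|---|---|---|---|
| 0 | any | 2.5% | 18% |
| 0.25 | 0.7 | 5.1% | 34% |
| 0.25 | 0.9 | 8.1% | 49% |
| 0.5 | 0.7 | 9.4% | 55% |
| 0.5 | 0.9 | 20% | 83% |

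Example for d = 0.25, r = 0.7: √0.6 = 0.775; 0.25 / 0.775 = 0.32; 1 − Φ(1.64) = 0.051; 1 − 0.949⁸ = 0.34.

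With 6 completers the last column becomes 14% at d = 0, 27% to 40% at d = 0.25 and 45% to 74% at d = 0.5. The calculation is for one measure and assumes independent participants. RCI holds the error rate at its nominal level only when d = 0. CSC is not defined further, and nothing in section 9.1 brings the pre-treatment course into it.

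**The case against.** The strongest reply is that this is a declared case series, in which lack of a control is inherent. Its primary aim is acceptability and feasibility. Efficacy is secondary and described as initial, and section 2 speaks of preliminary data and of potential to improve outcomes. The analysis is charts with RCI and CSC, and the reference in section 8 to measures throughout baseline might mean repeated readings. Most of this stands and limits how serious the point is. It does not remove it: no schedule supports the wording in section 8, and sections 4.2 and 9.1 still use the word efficacy.

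A reader might infer more than the documents support:

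- **That the phase comparison can never reach significance.** Section 9.1 contains no between-phase test and no alpha, so there is no significance threshold for it to miss. The FND questions also have two pre-treatment readings, not one.
- **That the size of regression to the mean can be stated.** The entry criterion requires current symptoms without a severity cut-off, and no retest data are given. The values of d above are assumptions, not estimates.
- **That section 7 attributes improvement to the intervention.** Its sentence on benefit is conditional and most naturally says that quality of life may improve following symptom improvement.
- **That a few more baseline readings would justify the word efficacy.** Without staggered starts or a control, they reduce the problem but do not exclude drift or regression to the mean.

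**Conclusion.** The point holds as an inconsistency between analysis and schedule that limits the secondary aim. Sections 8 and 9.1 presuppose a baseline phase; sections 2 and 6.3 provide one baseline completion. The result is two pre-treatment readings for the FND questions, one for CORE-10, EuroQol, CORE 34 and WSAS, and one or possibly two for SOMS-7. From these, the charts, RCI and CSC cannot distinguish change during treatment from earlier drift or regression to the mean.

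The counts come directly from the documents, on the reading that the weekly survey is also completed before session 1. The percentages rest on assumed reliability, assumed untreated improvement and a 1.96 threshold; they show only that a few participants classed as reliably improved would be weak evidence of a treatment effect. The primary aim is untouched, so this should be fixed but does not invalidate the study.

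**What to change.** In section 6.3, give the existing weekly Qualtrics outcome set (FND questions, CORE-10, EuroQol) at least three times at about weekly intervals before session 1, counting the pre-session-1 survey as the last. In section 9.1, chart each person's treatment readings against their own baseline level and range. A trend-adjusted index is not needed, since three points carry very little information on trend.

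In sections 4.2 and 9.1, describe the result as uncontrolled within-person change rather than efficacy. This applies even with the extra readings.

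If the extra readings are not adopted, remove the reference to a baseline phase from section 9.1, state that the analysis is uncontrolled pre-post change, and reconcile sections 2, 6.3, 8 and 9.1.

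The cost is two extra short online surveys and about two weeks' delay per participant, on a platform already in use. Vouchers depend on the percentage of measures completed, so the maximum stays at 8 × £45 = £360, although the count of measures behind the percentage must be updated. The rewording alone costs only an amendment.

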## **9.2 Sample Size:**

The appropriate sample size for a case series is variable depending on the type of study conducted and the depth of data yielded. Carey and Boden (2003), suggest that a case series can explore as few as two or three cases. This study will recruit 8 participants with a view to at least 6 participants completing the intervention. This ensures a larger sample than the minimum recommended in critical guides.

## **10) MONITORING AND QUALITY ASSURANCE**

The current study will be utilising clinical and research supervision to manage quality. Clinical supervision will be provided weekly during the intervention stage of the study. Supervision will follow an agenda which covers quality issues. Adherence and adverse events/reactions will be recorded and put in the study master file. Supervision will also be used to ensure all paperwork and governance is completed weekly.

## **11) SAFETY CONSIDERATIONS AND ADVERSE EVENTS**

The study is offering participants a novel treatment package focussing on improving the communication between body and brain through 6-8 sessions of psychological therapy. As with any novel psychological intervention, there is the potential that the intervention could cause an increase in symptoms or increase psychological distress. In order to protect participants from harm, adverse and serious adverse reactions will be monitored for all participants, including any changes in symptoms and risks to self or others. The research team will make every effort to prevent adverse reactions from happening. Further detail on the protocols is included in the Ethical Considerations section.

## **12) PEER REVIEW**

The current study was proposed to the University of Manchester Research Subcommittee Panel A in June 2022 for independent review. The panel provided feedback and amendments to the proposed study, these recommendations and feedback were then taken on board and a subsequent letter and proposal was submitted to the Research Subcommittee for further review. The Committee then wrote a letter stating that the research proposal has

been independently reviewed and that it is considered to meet necessary scientific and methodological standards.

### **13) ETHICAL AND REGULATORY CONSIDERATIONS**

#### **13.1 Approvals**

List the approvals that will be in place for your study and framework/principles to be followed during the study.

University Research Ethics Committee approval will be obtained before commencing research. The study will be conducted in full conformance with all relevant legal requirements and the principles of the Declaration of Helsinki, Good Clinical Practice (GCP) and the UK Policy Framework for Health and Social Care Research 2017.

#### **13.2 Risks**

The study is offering participants a novel treatment package focussing on improving the communication between body and brain through 6-8 individual sessions of psychological therapy.

Prior to commencing treatment, participants GP' (with consent from participant) will be sent a letter advising them that the participant has agreed to participate in the study and engage with novel psychological intervention for FND. A protocol for managing risks throughout the study has been generated and includes the procedures for if participants disclose information containing risks to themselves or others (including contacting participant GP, signposting to additional support for participants). Any risks, adverse reactions or serious adverse reactions will be taken to clinical supervision and discussed with the research team.

The intervention for the study will be delivered by a Trainee Clinical Psychologist (principal researcher) under the close supervision of the Primary Academic Supervisor (who is a qualified Clinical Psychologist). In the event of a participant experiencing serious adverse reactions to the treatment delivered, a protocol will be activated whereby the research team will consider stopping the trial. The research team will consider withdrawing treatment from participants not experiencing serious adverse reactions following evaluating severity of risks. Decisions around proceeding or stopping the trial will involve an independent academic from within the Division of Psychology and Mental Health at the University of Manchester. Any decisions around stopping the trial will take into account the impact on other participants and risks of this will be mitigated accordingly (through offering additional generic support, signposting to support and alternative non-direct counselling or support). Whilst the principal researcher has developed protocols to manage and mitigate any risks to participants, we have no reason to believe this therapy will carry any higher risk than any other therapy that is regularly offered to individual's with FND. Any adverse event, reaction, serious adverse event or reactions occurring for participants will be logged and documented and the outcome of decision making around each reaction will also be logged and stored in order to monitor the overall wellbeing of participants in the study. The information sheet will also emphasise that the intervention offered is a novel treatment that is aiming to gather initial evidence as

to its effectiveness, this is to fully inform participants of the nature of the intervention being delivered and manage expectations around its effectiveness so that participants can make informed choices around consenting to participate. Furthermore, at the end of the intervention, the principal researcher will discuss future options with participants including signposting to further support services as appropriate.

There is the potential as with any psychological intervention that the principal researcher could become distressed or affected by the delivery of intervention. This will be mitigated by the principal researcher being closely supervised by a qualified Clinical Psychologist throughout the delivery of intervention. No other risks to researchers have been identified

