### **6.2 Exclusion Criteria:**

Participants will not be eligible to participate in the study if they:

- Are currently undergoing any other psychological therapy
- Have previous experience of a mindfulness-based intervention targeting FND. The intervention tested utilises a mindfulness-based approach, so previous experience of this

would affect the acceptability of the intervention if participants have already engaged in something similar.

- have symptoms of epilepsy and/or loss of consciousness, as treatment sessions will be provided remotely and this impacts on our ability to support and manage risks of individuals that may lose consciousness in a session.
- have symptoms of psychosis (as assessed on the Comprehensive Assessment of At-Risk Mental State, CAARMS), as individuals with both FND and psychosis symptoms would make the sample non-homogenous. Furthermore, individuals with active psychosis are likely to experience more serious adverse reactions and may struggle to engage in the treatment package offered.
- have a diagnosis of Personality Disorder, as they are more likely to experience more serious adverse reactions and may struggle to engage in the treatment package.
- have active plans of self-harm and/or suicide. Potential participants will be asked to complete the risk items on the CORE-OM and will be interviewed around these. This is to ensure the safety of participants engaging in novel therapy and to manage the risks of any potential adverse side-effects of therapy
- Have a history of prior suicide attempts, to manage the risks of causing negative side effects of therapy
- Have any difficulties with alcohol or substance misuse, as this would make the sample non-homogenous. Furthermore, difficulties with alcohol and substance use could impact on ability to engage in the treatment package and also this population could experience more serious adverse reactions.
- Have active symptoms of Post Traumatic Stress Disorder (PTSD) i.e., having current symptoms of nightmares and flashbacks. This population would be more at risk of adverse effects and would make the sample non-homogenous.
- Have symptoms of an eating disorder. This would make the sample non-homogenous and this population would be more at risk of adverse effects.

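### Other treatment is controlled only at entry and not systematically recorded afterwards, so individual change, especially at the one-month follow-up, cannot be told apart from changes in other care

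*Combined protocol and SAP*

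**What the plan says.** **Entry.** Section 6.2 excludes people who "Are currently undergoing any other psychological therapy" or who "Have previous experience of a mindfulness-based intervention targeting FND". Sections 6.1 and 6.2 do not mention medication, physiotherapy or other FND care, and no section covers treatment begun after enrolment.

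**Data collected.** Sections 5.2 and 6.3 list the measures at each time point, and none is a treatment-use item. Section 8 describes the content as FND symptoms, "mental health and quality of life will also be collected and stored", besides identifying details and session recordings.

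**Contact with other services.** Section 13.2 provides for "contacting participant GP, signposting to additional support for participants" when risk is disclosed. For the close of therapy it states that "at the end of the intervention, the principal researcher will discuss future options with participants including signposting to further support services as appropriate".

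**Follow-up.** Section 5.2: "One month following the end of psychological therapy, a session will be attended remotely via Microsoft Teams by participants". All earlier measures are given again at that session.

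**Analysis.** For the efficacy question, section 9.1 will "chart individual participant FND symptoms and clinical measures during the baseline and treatment phases to determine any change in these variables" and will calculate RCI and CSC. It says nothing about other treatment.

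**The concern.** The exclusion in section 6.2 shows that the authors regard concurrent psychological therapy as something that would affect the study. From the first session onward, however, nothing in the data set would reveal that such therapy, or a new medicine or a course of physiotherapy, had started.

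In a case series the evidence is each person's own trajectory. There is no comparator, and baseline is taken at one pre-treatment meeting, so a reader of a chart needs to know what else changed for that person and when. If another treatment began in week 4, a later reliable change would look the same as one that followed the sessions alone. The one-month point is more exposed, because the study itself raises further support with participants shortly before it. Dated information of this kind is easy to collect at the time and hard to recover reliably afterwards.

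**Working it through.** The plan states no figure on this point. Its sample size (section 9.2: 8 recruited, at least 6 expected to complete) rests on case-series guidance, with no power calculation to reproduce. The check is therefore mainly a reading of the sections side by side.

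**Step 1. Is other treatment recorded anywhere?**

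| Time point | Listed content | Other treatment? |
|---|---|---|
| Screening (6.2, 6.3) | Eligibility questionnaire and meeting | Current psychological therapy and earlier mindfulness work for FND, as exclusions only |
| Baseline (6.3) | CORE 34, five FND questions, SOMS-7, WSAS | Not listed |
| Weekly (5.2) | CORE-10, FND questions, EuroQol, adverse reactions | Not listed |
| Final session (5.2) | Baseline measures again, satisfaction, acceptability | Not listed |
| Follow-up (5.2) | All of the above again | Not listed |
| Safety log (10, 13.2) | Adverse events and reactions, and decisions on them | Only where tied to an adverse event |

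A new prescription or course of counselling unrelated to an adverse event would appear in none of these.

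**Step 2. Which comparisons are exposed, and by what route?**

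- Baseline to end of treatment: concurrent care that starts, stops or changes during therapy, and signposting or GP contact after a risk disclosure. The end-of-therapy discussion cannot act here, because post-treatment measures are taken in the final session, before any support discussed could be taken up.
- End of treatment to follow-up: the same routes, plus any support taken up after the end-of-therapy discussion.

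**Step 3. How long is the exposed period?** Section 5.2 offers 8 weekly sessions; sections 2, 4.1 and 11 say 6 to 8. With a month taken as about 4 weeks, the period is 6 + 4 = 10 to 8 + 4 = 12 weeks.

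**Step 4. How much does one case weigh?** One affected person is 1/8 = 12.5% or 1/6 = 16.7% of the cases; two are 2/8 = 25% or 2/6 = 33.3%. These are shares of the series. They are the most that a responder proportion could move, reached only if each affected person's classification turned entirely on the other treatment.

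**Step 5. How likely is at least one affected case?** The documents give no uptake rate, so q, the chance that one person takes up other support, is an assumption. With independent participants, P(at least one) = 1 − (1 − q)^n.

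| q (assumed) | n = 6 | n = 8 |
|---|---|---|
| 0.05 | 0.265 | 0.337 |
| 0.10 | 0.469 | 0.570 |
| 0.20 | 0.738 | 0.832 |
| 0.30 | 0.882 | 0.942 |

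For example, at q = 0.10 and n = 8: 1 − 0.9^8 = 0.570. Even modest uptake makes an affected case about as likely as not, and the planned data would not show which case it was.

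**The case against.** The strongest reply is that this gap is not what stands between the study and a causal claim. An uncontrolled series with one baseline meeting cannot separate the package from natural fluctuation, regression to the mean or therapist contact, however complete the treatment records. RCI and CSC address whether change is reliable and clinically meaningful, not what caused it. Sections 2, 4.2 and 7 describe the efficacy evidence as initial or preliminary. All of this stands. It lowers the stakes, but this rival explanation remains one that the study could observe cheaply.

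A reader might also infer more than the documents support:

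- *That end-of-therapy signposting undermines all the symptom change.* It can affect only follow-up. The charting described in section 9.1 covers baseline and treatment; RCI and CSC have no stated time points, and no follow-up analysis is named. The follow-up outcomes will nevertheless exist and will need interpreting.
- *That every participant is sent to other services.* The discussion is general; signposting is given as appropriate.
- *That the GP letter, or the support described in case the trial is stopped, amounts to co-treatment.* The letter informs the GP of participation, and nothing says it triggers care. The stopping provision is a contingency.
- *That nothing is ever recorded.* Screening must elicit current psychological therapy, and decisions on adverse reactions are logged. General uptake of other care is still not captured.

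Risk-triggered signposting should also be less common than it might appear, because section 6.2 excludes active plans of self-harm or suicide, previous attempts, active PTSD symptoms and substance misuse.

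**Conclusion.** The point holds as a limit on interpretation. Other psychological therapy is controlled only at entry, other forms of care are not addressed at all, and no listed measure systematically records treatment use afterwards. Individual change during therapy cannot be distinguished from concurrent treatment changes, and follow-up change or maintenance cannot be distinguished from support taken up after therapy ended.

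Its size is modest and uncertain. The case shares in step 4 follow directly from the planned numbers; the probabilities in step 5 depend on an assumed uptake rate and on independence between participants. Neither shows that bias will occur, nor its direction. The effect falls on the secondary aim and leaves the primary aim largely untouched. It is worth changing because it is inexpensive and must be in place before baseline collection to be complete. The documents do not support saying that this gap alone prevents attribution, or that closing it would permit attribution.

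**What to change.** - **Baseline survey:** add a brief item on current treatment, covering medication, physiotherapy or other FND care, and psychological support.
- **Weekly and follow-up Qualtrics surveys:** add one line asking what treatment or support was started, stopped or changed since the last survey, and when. At follow-up, also ask whether any signposted support was taken up.
- **Section 9.1:** mark these dates on each participant's chart. Report beside the RCI/CSC results which cases had a treatment change before each assessment. State that follow-up change may reflect other support.
- **Interpretation:** do not treat cases without recorded changes as proof that the package caused the change.

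No change to care, signposting, eligibility or sample size is needed. The cost is about a minute of participant time per survey (with 8 sessions, 1 + 8 + 1 = 10 surveys, so about ten minutes per person in total) and slightly more cautious efficacy wording.
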